6.2.6 Visit 5/Week 8 (Day 57 ±5)

The following procedures must be performed and recorded at the Week 8 visit.

1. Obtain pregnancy test and evaluate results, as applicable. If pregnancy test is positive, the subject may continue in the study; however, study drug should be discontinued.
2. Perform lesion mapping and update lesion map with location for any new lesions.
3. Perform scarring/keloid assessment.
4. Weigh returned study drug and review study compliance.
5. Weigh, record, and dispense new supply of study product and dispense subject diary.

6. Review dosing instructions and have subject/caregiver apply daily dose in clinic using the newly dispensed kit.
7. Perform BOTE Inflammation Score (post-dose).
8. Perform Local Skin Reaction Assessment (post-dose).
9. Collect and record AE information for AEs reported.
10. Update concomitant medication information and confirm if any new occurrences of MC were reported in the subject's household.

6.2.7 *Visit 6/Week 12/ET (Day 85 ±5)*

The following procedures must be performed and recorded at the Week 12/ET1 visit.

1. Complete age-matched Dermatology Life Quality Index (DLQI) assessment, as applicable.
2. Obtain pregnancy test and evaluate results, as applicable.
3. Perform lesion mapping and update lesion map with location for any new lesions.
4. Perform scarring/keloid assessment
5. Perform a brief physical examination.
6. Subject/caregiver administer final dose of study drug from previously dispensed kit.
7. Perform BOTE Inflammation Score (post-dose).
8. Perform Local Skin Reaction Assessment (post-dose).
9. Weigh returned study drug and review study compliance.
10. Collect and record AE information for AEs reported.
11. Update concomitant medication information and confirm if any new occurrences of MC were reported in the subject's household.

6.2.8 *Visit 7/Week 16 and Visit 8/Week 20 (Day 113 +/- 7 days; Day 141 +/- 7 days)*

The following procedures must be performed and recorded at the Week 16 and Week 20 visits. It is expected that these visits should be done by telephone.

1. Collect and record information for new and ongoing AEs, including recurrence of MC.
2. Update concomitant medication information.

6.2.9 *Visit 9/Week 24 (Day 169 +/- 7 days)*

The following procedures must be performed and recorded at the Week 24 visit.

1. Perform scarring/keloid assessment.
2. Collect and record information for new and ongoing AEs, including subject recurrence of MC.

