7.2.4 Local Skin Reaction Score

The investigator (or designated evaluator) will assess localized skin reactions (LSRs) at Baseline (at least 30 minutes post-dose), and at Weeks 2, 4, 8 and 12. The individual components of LSRs are scored separately on a scale of 0-4, with higher numbers indicating more severe reactions. The individual components include erythema, flaking/scaling, crusting, swelling, vesiculation/pustulation, and erosion/ulceration.

Compared to BOTE, LSR is generally more diffuse, associated with significant itch or tenderness, may necessitate discontinuation of study treatment and may need treatment for symptomatic relief (e.g. a topical corticosteroid or topical anesthetic). For very severe LSR, systemic corticosteroids may be considered.

Investigators will assess the treatment area at each scheduled visit and use their medical judgement to differentiate between BOTE and LSRs. When LSRs are clinically significant in the opinion of the investigator, s/he should report the condition as an AE(s) (e.g. application site erythema, application site edema).

In the event of an LSR, the investigator may choose to initiate a drug holiday for the study drug for up to 2 weeks; treatment with corticosteroids may be ordered during the drug holiday at the investigator's discretion. For very severe LSR, systemic corticosteroids may be considered. The subject should be instructed how many days to hold study drug and site staff should phone the

subject on the planned day of resuming study drug to ensure that the LSR has resolved. If the LSR has not resolved, the drug holiday may be extended as long as the total period of withholding study drug does not exceed 2 weeks. If the LSR has resolved, the subject may resume treatment. If the LSR flares again after re-introduction of study drug, allergic contact dermatitis may be suspected. The subject may again be treated with up to 2 weeks of corticosteroids.

If allergic contact dermatitis is suspected, study drug should be discontinued permanently and an AE of allergic contact dermatitis should be recorded as the reason for discontinuation. Week 12/ET1 assessments should be completed at the time of discontinuation, but the subject should continue in the study and complete study-related visits through Week 24.

Patch testing (see [Section 7.2.5](#) and [Section 20.2](#)) should be offered to the subject.

LSR Score

	Erythema	Flaking/ Scaling	Crusting	Swelling	Vesiculation/ Pustulation	Erosion/ Ulceration

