7.2.5 Patch Testing

In the event that a subject has an LSR that is felt to be suggestive of allergic contact dermatitis, patch testing may be initiated to confirm. This should be offered to the subject/caregiver. If the subject/caregiver consents to patch testing and once the LSR has been completely resolved for a period of 2 weeks and up to 2 months, patch testing will commence. Novan will provide the patch testing instruction once requested from the CRO medical monitor. Additional drug product for

patch testing may be supplied through IWRS if the currently assigned subject's investigational product has been assignment was > than 60 days of the patch testing date(s).

If allergic contact dermatitis is suspected, study drug should be discontinued permanently and an AE of allergic contact dermatitis should be recorded as the reason for discontinuation. Week 12/ET1 assessments should be completed at the time of discontinuation, but the subject should continue to participate in the study and complete study related visits through Week 24.

In the event of suspected allergic contact dermatitis, photographs may be taken of the affected area(s) and transmitted to the CRO medical monitor for review prior to initiating patch testing.

See [Section 20.2](#) for further information.

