7. NOTATION OF TREATMENT GROUPS AND VISITS

Analysis visits

Baseline is defined as the last nonmissing value recorded prior to the first application of study drug. If time is not recorded and the assessment was on the same day as the first application of study drug, then it will be assumed the assessment occurred prior to the application of study drug. The baseline record will have an analysis visit of “Baseline”.

For all evaluations of all parameters, assessments will be analyzed according to the visit at which they occurred (i.e., per the eCRF visit label). In order to account for the fact that the Week 12 and Early Termination visits are collected on the same eCRF in the database, a check against the Study Exit form will be made to determine if the visit is a Week 12 or an Early Termination Visit. If the visit is an Early Termination visit, then the visit will be mapped according to the table below. If there is no corresponding Study Exit form on the same date, then it will be considered a Week 12 visit. If there is no assessment in a given visit, then the following visit windows will be applied to determine if an unscheduled visit may be used:

Visit	Analysis Visit	Target Study Day	Study Day Analysis Window
Week 2 (± 3 days)	Week 2	15	Day 12 to 22
Week 4 (± 5 days)	Week 4	29	Day 23 to 43
Week 8 (± 5 days)	Week 8	57	Day 44 to 71
Week 12 (± 5 days)	Week 12	85	Day 72 to 98

Days are measured from the date of randomization. Study days corresponding to measurements are calculated as:

- Assessment date – date of randomization + 1, if assessment date is on or after the date of randomization.
- Assessment date – date of randomization, if measurement date is before the date of randomization.

In the event of multiple unscheduled records falling in the same analysis window, the assessment which is closest to the target study day will be chosen for analysis.

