9.5 Protocol Deviations

Significant protocol deviations that could potentially affect the efficacy or safety conclusions of the study will be identified prior to database lock and unblinding of individual subject treatment information. Significant protocol deviations may include, but are not limited to:

- Randomly assigned subjects who did not satisfy selected inclusion and exclusion criteria
- Randomly assigned subjects who developed withdrawal criteria during the study but were not withdrawn
- Subjects who were randomized incorrectly including subjects of the same household who are randomized to different treatments
- Subjects who received the wrong treatment
- Subjects where the subject/site staff were unproperly unblinded
- Week 12 Lesion Count not performed
- Subjects who received an excluded concomitant treatment.

The decision on the criteria for whether a subject is excluded from the PP Population will be made during the data review meeting prior to unblinding and database lock. Reasons for exclusion of a subject from the analysis will be listed.

A listing of all protocol deviations including the deviation designation (major or minor and significant or not), category, and indication of whether the deviation led to an exclusion of a subject from the PP Population will be presented in a data listing.

Major and significant protocol deviations will be summarized by deviation category and treatment group.

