10.4 Handling of Dropouts or Missing Data

In analyses based on response, a missing response will be considered a nonresponder.

For a sensitivity analysis, subjects with missing lesion count at Week 12 but who demonstrated complete clearance at the last collected lesion assessment will be counted as responders.

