Where the SE =

$$\sqrt{\frac{p_{SB206}^2(1-p_{SB206})^2 s_{SB206}^2 + p_{Vehicle}^2(1-p_{Vehicle})^2 s_{Vehicle}^2 - 2p_{SB206}(1-p_{SB206})p_{Vehicle}}{(1-p_{Vehicle}) * \left(\frac{s_{SB206}^2 + s_{Vehicle}^2 - s_{Odds\ Ratio}^2}{2} \right)}}$$

The p_{SB206} and $p_{Vehicle}$ are the transformed predicted log odds at the mean of the covariates, s^2 's are the standard errors of the predicted log odds and the odds ratio.

As a sensitivity analysis, the above primary analysis model will be applied to the PP Population. An additional sensitivity analysis counting subjects who discontinued prior to Week 12 or have a missing lesion count assessment but who demonstrated complete clearance at the last collected lesion assessment as responders will be presented. The impact of mis-stratifications may be explored via a sensitivity analysis.

An analysis where the complete clearance response probability for each dropout prior to Week 12 will be independently generated across the following scenarios (Vehicle response probability, SB206 response probability):

(0.1, 0.1)	(0.1, 0.0)			
(0.2, 0.2)	(0.2, 0.1)	(0.2, 0.0)		
(0.3, 0.3)	(0.3, 0.2)	(0.3, 0.1)	(0.3, 0.0)	
(0.4, 0.4)	(0.4, 0.3)	(0.4, 0.2)	(0.4, 0.1)	(0.4, 0.0)

The analysis will be produced 100 times and then the results for the estimated log odds ratio for treatment and its estimated standard error from each of the imputations will be combined using PROC MIANALYZE.

An additional sensitivity analysis will be performed in a subset of the ITT population where only 1 subject from each household is chosen to contribute to the model based on the subject with the highest number of baseline treatable MC and the oldest to break ties, if needed. A logistic regression model including treatment, investigator type, age, and baseline lesion counts will be utilized.

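### SAP section 7 sets no study-day limit when it labels a shared Week 12/ET form as Week 12, so a lesion count taken at an early treatment stop could become the primary-endpoint record (minor fix)

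*Combined protocol and SAP*

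**What the plan says.** - **Labelling rule (final SAP, section 7).** Assessments are analysed by eCRF visit label. Week 12 and Early Termination use the same form, so the SAP looks for a Study Exit form. If one carries the same date, the record is an Early Termination visit and is mapped by study day (Week 4: Day 23 to 43; Week 8: Day 44 to 71; Week 12: Day 72 to 98). Otherwise: "If there is no corresponding Study Exit form on the same date, then it will be considered a Week 12 visit".
- **Several records (same section).** The only selection rule is this: "In the event of multiple unscheduled records falling in the same analysis window, the assessment which is closest to the target study day" is chosen.
- **Treatment stop without study exit.** Protocol 7.2.4, on suspected allergic contact dermatitis: "Week 12/ET1 assessments should be completed at the time of discontinuation, but the subject should continue in the study". Protocol 7.2.5 repeats it: "Week 12/ET1 assessments should be completed at the time of discontinuation, but the subject should continue to participate in the study". Both continue visits through Week 24.
- **One combined visit.** Protocol 6.2.7: "The following procedures must be performed and recorded at the Week 12/ET1 visit". Table 1 includes a lesion count at that visit.
- **Missing data (SAP 10.4).** "In analyses based on response, a missing response will be considered a nonresponder".

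**The concern.** The Study Exit check identifies people who leave the study. A subject who stops study drug for suspected contact dermatitis but stays in the study has no reason to have a Study Exit form that day. If the stop assessment is entered on the shared form, the rule labels it Week 12 whatever its date.

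The label decides which lesion count is the primary-endpoint record. Two gaps follow. If no later count exists, the early count stands as an observed Week 12 result and the nonresponder rule is not reached. If a true Week 12 count also exists, two records carry the label, and the SAP's selection rule covers unscheduled records only.

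**Working it through.** **1. Tracing the rule.** Take a Week 12/ET1 form dated Day 30.

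- With a same-date Study Exit form, it is an Early Termination visit and maps to Week 4 (Day 23 to 43).
- Without one, it is labelled Week 12, although the Week 12 window opens 72 − 30 = 42 days later.

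**2. When responder status changes.**

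| Early count | True Week 12 count | Result if early record is used | Result from the true count, or from 10.4 | Changed? |
|---|---|---|---|---|
| Nonzero | Missing | Nonresponder | Nonresponder | No |
| Nonzero | Nonzero | Nonresponder | Nonresponder | No |
| Nonzero | Zero | Nonresponder | Responder | Yes |
| Zero | Zero | Responder | Responder | No |
| Zero | Nonzero | Responder | Nonresponder | Yes |
| Zero | Missing | Responder | Nonresponder | Yes |

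Where both counts exist, a change also requires that the early record is the one selected, which the SAP leaves open.

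**3. Reproducing the planned power.** Inputs from SAP section 5: 227 SB206, 113 vehicle, 36% against 18%, two-sided 0.05. With pooled variance under the null, power = Φ[(d − 1.96·SE0)/SE1].

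- Pooled rate = (113 × 0.18 + 227 × 0.36)/340 = 0.3002
- SE0 = √[0.3002 × 0.6998 × (1/113 + 1/227)] = 0.0528
- SE1 = √[0.18 × 0.82/113 + 0.36 × 0.64/227] = 0.0482
- Power = Φ[(0.18 − 1.96 × 0.0528)/0.0482] = 94.4% (SAP: 94%)

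The same formula gives 93.4% and 82.8% for the other two scenarios (SAP: 93% and 83%).

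**4. Size per subject.** One reversed SB206 subject moves that arm by 1/227 = 0.44 points; one vehicle subject moves its arm by 1/113 = 0.88 points. One SB206 responder lost (36.00% to 35.56%) takes power from 94.4% to 93.4%.

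**5. How many subjects.** The documents give no rate of suspected contact dermatitis. Protocol 1.2.2 reports no adverse-event treatment stops among the 48 Phase 2 subjects on 12% QD. The exact 95% interval for 0/48 is 0 to 7.4%.

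For illustration only, assume the application-site stops across all active Phase 2 arms apply here:

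- Active subjects (protocol 1.1): 47 + 48 + 47 + 48 = 190; 6/190 = 3.16%
- 227 × 3.16% = 7.2 SB206 subjects
- Suppose every early count is nonzero and is used, and 0 to 18% of these subjects are clear at the true Week 12 (18% is the vehicle planning rate, taken because treatment has stopped)
- Responders lost: 0 to 7.2 × 0.18 = 1.29, or 0 to 0.57 points
- Power at 35.43% against 18%: 93.1%

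In the other direction, the documents give no rate for an early zero followed by new lesions or by a missing count. Each such SB206 subject would add 0.44 points.

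**The case against.** **The decisive link is unseen.** The problem arises only if sites use the shared form. Protocol 7.2.4 and 7.2.5 say which assessments to do, not how to record them. Where the protocol says a visit is recorded as ET1 (4.1), it means subjects leaving the study. Table 1 allows unscheduled visits for medical reasons, and for such a visit the windows would apply. The annotated eCRF and the dataset specifications could settle this and are not supplied. This stands, and it is why the point is conditional.

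**Other safeguards exist.** SAP section 6 lists subjects with reactions suggestive of contact dermatitis for narratives, and derived datasets are double-programmed (Appendix C). The per-protocol analysis may exclude these subjects if "Week 12 Lesion Count not performed" is flagged for them. SAP 11.1 adds another route: "An additional sensitivity analysis counting subjects who discontinued prior to Week 12 or have a missing lesion count assessment" but whose last count was clear, as responders; it reaches them if discontinuing includes stopping treatment. These make silent misclassification less likely. None changes the label in the primary ITT analysis.

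**The effect is close to nil.** All seven Phase 2 adverse-event stops were in BID arms, and none is described as contact dermatitis. This stands too, and it sets the severity.

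**Stronger readings.** A reader might infer a material loss of power. Setting 7.4% of SB206 subjects as affected, all with nonzero early counts used and 36% of them truly clear, gives 86.1%. That stacks the upper limit from 0/48 on a full treatment response in people who have stopped treatment, and nothing in the documents supports the combination. A reader might also note that, against 20/113 on vehicle, an unadjusted pooled test gives p = 0.042 with 63/227 and p = 0.051 with 62/227. That holds for any single subject in a borderline result and says nothing about this rule.

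**Conclusion.** The gap is real but minor. As written, section 7 can make an early lesion count the primary-endpoint record for a subject who stops treatment and stays in the study, provided sites used the shared form.

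The expected effect is very small. Phase 2 experience on 12% QD points to no affected subjects, and the illustration gives at most 0.57 points and a power of 93.1% instead of 94.4%. That figure rests on a borrowed stop rate from a group wider than suspected contact dermatitis.

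The documents do not show that any subject will be mislabelled, nor that the error favours one arm: status can change in either direction. A reader might also infer that the protocol contradicts itself on ET1. It does not: 4.1 covers leaving the study, while 6.3.1, 7.2.4 and 7.2.5 cover stopping treatment.

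**What to change.** Add three rules to SAP section 7 before unblinding:

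1. A Week 12/ET form completed because treatment was stopped early, in a subject who remains in the study, is mapped by the existing window table in the same way as an Early Termination visit. It fills a window only if the scheduled visit there has no assessment.
2. A scheduled Week 12 visit keeps its label whether it is early or late, and takes precedence if more than one record could be Week 12. If there is none, use the record closest to Day 85, and the later one if tied.
3. A subject left with no Week 12 count is missing, hence a nonresponder under 10.4, and enters the existing missing-count sensitivity analysis.

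Checks on the rules:

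- Stop count on Day 30, nothing later: Week 12 is missing, nonresponder.
- Stop on Day 30, scheduled visit on Day 85: Day 85 is used.
- Stop on Day 83, scheduled visit on Day 88: Day 88 is used.
- Days 80 and 90, neither a scheduled Week 12 visit (both 5 days from target): Day 90 is used.
- Scheduled Week 12 visit on Day 70 or Day 100: it stays Week 12.

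The rule is confined to treatment-stop forms on purpose. A blanket cut-off at Day 72 would strip the label from a genuine scheduled visit held slightly early. The mapping of true Early Termination visits stays as written.

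Cost: three short rules and one derivation in the analysis dataset. No new data, no change in sample size and no protocol change.

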8. ANALYSIS POPULATIONS

The following subject population will be used for disposition analyses:

- The Enrolled Population will consist of all subjects who have a signed informed consent or assent. If a subject is randomly assigned to a treatment, then treatment assignment will be based on randomized treatment; otherwise, they will be deemed a screen failure and will only appear in the overall summary columns of output.

The following subject population will be used for safety analyses:

- The Safety Population will consist of all subjects who receive at least 1 application of study medication. Treatment assignment will be based on the treatment actually received. If a subject receives any amount of SB206, then they will be summarized in the SB206 12% QD arm.

The following subject populations will be used for efficacy analyses:

- The ITT Population will consist of all subjects who are randomized. Treatment assignment will be based on the randomized treatment.
- The Per-Protocol (PP) Population will consist of all subjects in the ITT Population who had no significant protocol deviations that impacted the analyses of efficacy endpoints. Final determination of subject inclusion in the PP Population will be made prior to unblinding. Treatment assignment will be based on the randomized treatment.

9. STUDY POPULATION

9.1 Subject Disposition

Subject disposition information will be summarized for all subjects by treatment group. Summaries will include: the number of subjects screened, the number of subjects in each analysis population, the number of subjects where study treatment stopped, primary reason for study treatment stopped, the number of subjects completing 12 weeks of the study (defined as having an end of treatment reason of “Completed Treatment Per Protocol” or a reason of “Complete Clearance Prior to Week 12” and does not have a Study Exit date prior to the subject’s Week 12 visit date), the number of subjects completed the study, and the primary reason for discontinuation.

A summary of the number of subjects in each center and each population will be presented.

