6.3 Discontinuation

6.3.1 *Treatment Discontinuation*

If at any time during the study the investigator determines that it is not in the best interest of the subject to continue treatment, the subject's treatment will be discontinued. The investigator can discontinue the treatment for a subject at any time if medically necessary. If a subject's treatment is permanently discontinued by the investigator because of an AE, that AE should be indicated as the reason for treatment discontinuation. In this case, the subject is discontinued from the treatment, but still participates in the study and the subject is encouraged to follow the visit schedule and complete all assessments.

In addition, the investigator may instruct the subject to temporarily halt treatment of a specified region (i.e., due to an adverse event). This treatment modification and the reason for the temporary drug interruption should be documented in the subject's source documents and eCRF. The lesions in the impacted area should continue to be counted in the lesion count during the period of treatment modification.

The investigator may discontinue a subject's treatment if the subject/caregiver has failed to follow study procedures or to keep follow-up appointments. Appropriate documentation in the subject's study record and the study database regarding the reason for treatment discontinuation must be completed.

Reasons for an investigator's withdrawal of a subject **from the treatment** may include, but are not limited to, the following:

- Safety (e.g., severe adverse reactions, pregnancy)

- When a concomitant medication or treatment likely to interfere with the results of the study is reported, or required, by the subject, the investigator will decide, in consultation with the CRO whether the subject is to be withdrawn.

Reason(s) for discontinuation from the treatment as listed in the study record will be entered into the study database as follows:

- Completed (complete clearance prior to Week 12)
- Adverse Event (including LSRs deemed to be significant by investigator)
- Withdrawal by Subject/Caregiver
- Physician Decision
- Protocol Violation
- Lost to Follow-Up
- Pregnancy
- Lack of Efficacy
- Worsening of Molluscum Contagiosum
- Other

6.3.2 *Study Discontinuation*

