During the study, females 9 years of age and older should be instructed to contact the investigator immediately if they suspect they might be pregnant (e.g., missed or late menstrual cycle). Study drug shall be held immediately if a subject is suspected to be pregnant and study drug must be permanently discontinued if pregnancy is confirmed. The Investigator must immediately notify the medical monitor/CRO of any female subject who becomes pregnant any time during study participation, record the information on the pregnancy notification form and email the form to the CRO. Subjects found to be pregnant prior to Week 12 will stop study drug treatment, continue with study visits through Week 24 and follow up with pregnancy outcome. Beyond Week 24, the site should follow-up with the subject periodically during the pregnancy for ongoing health and safety information through the end of the pregnancy, as applicable. The investigator is responsible for following the pregnancy through the end of the pregnancy and for providing the assessment of the healthy live birth or for reporting any abnormal outcome such as stillbirth, miscarriage, or deformity to the CRO/Sponsor (Note: Congenital anomaly/birth defect/ etc. are considered SAEs and require separate reporting per [Section 10](#).)

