If a subject's treatment is discontinued by the investigator or the subject because of an AE, that AE should be indicated as the reason for treatment discontinuation. All subjects will be encouraged to remain in the study throughout the 24-week study duration.

When approximately 200 subjects (cumulative across studies MC301 and MC302) have completed 4 weeks of treatment, a data safety monitoring board (DSMB) will review all available unblinded safety data (including patch testing).

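### SAP 9.1 defines completing 12 weeks of the study by the reason treatment stopped, so subjects who stop drug but attend Week 12 are reported as non-completers

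*Combined protocol and SAP*

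**What the plan says.** SAP 9.1 (Subject Disposition) lists among its summaries "the number of subjects completing 12 weeks of the study (defined as having an end of treatment reason of" one of two values: treatment completed per protocol, or complete clearance before Week 12. It adds a condition that the subject "and does not have a Study Exit date prior to the" Week 12 visit date. The two earlier SAP versions in the file break this condition off mid-phrase. The final version completes it and is the one considered here.

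The protocol keeps treatment and study participation apart:

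- Section 6.3.1, on a permanent stop for an adverse event: "the subject is discontinued from the treatment, but still participates in the study and the subject is encouraged to follow the visit schedule".
- Sections 7.2.4 and 7.2.5, on suspected allergic contact dermatitis: drug stops for good, the Week 12/ET1 assessments are done at that point, and visits go on to Week 24.
- Section 9.5, on subjects found pregnant before Week 12: they "will stop study drug treatment, continue with study visits through Week 24 and follow up with pregnancy outcome".
- SAP section 4, in general: "All subjects will be encouraged to remain in the study throughout the 24-week study duration".

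The treatment-stop reasons in protocol 6.3.1 also include physician decision, lack of efficacy and worsening of molluscum. None of these qualifies under SAP 9.1.

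**The concern.** The line is labelled as study completion but is built from a treatment variable. A reader of the disposition table will take it as the share of each arm followed to the primary time point. Subjects who stopped drug and stayed, as the protocol asks, are removed from that share although their Week 12 count was observed.

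The error can differ between arms. Stops for tolerability would be expected more often on active gel, and stops for lack of efficacy perhaps more often on vehicle. The table could then show a retention difference that did not occur, or hide one that did.

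The exit condition raises a second, smaller question. It compares the Study Exit date with the Week 12 visit date, but a subject who has left will usually have no Week 12 visit.

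**Working it through.** The plan gives no figure to reproduce, so the rule itself was tested. Let A = treatment completed per protocol, B = stopped for clearance before Week 12, and C = Study Exit dated before the Week 12 visit. The sentence in SAP 9.1 can be read in two ways:

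- Reading 1: A or (B and not C)
- Reading 2: (A or B) and not C

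Each cell gives the result under reading 1 / reading 2.

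| End-of-treatment reason | Week 12 attended, no earlier exit | Exit dated before Week 12 visit | Left, no Week 12 visit date |
|---|---|---|---|
| Completed per protocol | completer / completer | completer / not | completer / undefined |
| Clearance before Week 12 | completer / completer | not / not | undefined / undefined |
| Any other reason | **not / not** | not / not | not / not |

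**Other reason, Week 12 attended.** The subject is a non-completer under both readings. This is the error, and it does not depend on how the sentence is parsed.

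**Clearance, exit before the Week 12 visit.** The subject is a non-completer under both readings, which is correct.

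**Clearance, no Week 12 visit date.** The result is undefined, because C cannot be evaluated and SAP 9.1 gives no fallback date. SAP 7 notes that "the Week 12 and Early Termination visits are collected on the same eCRF in the database" and separates the two by a Study Exit form on the same date. An early termination visit is then mapped by study day, so one on Day 50 falls in the Week 8 window (Day 44 to 71) and leaves no Week 12 date.

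**Size of the first error.** The only rates in the documents are Phase 2 adverse-event treatment stops (protocol 1.1 and 1.1.4):

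- Active arms: 47 + 48 + 47 + 48 = 190 subjects; 3 + 2 + 2 + 0 = 7 stops; 7/190 = 3.7%.
- 12% QD alone: 0/48.
- Vehicle: 0/66.

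Applied to the planned 227 SB206 subjects, the range is 227 × 0 = 0 to 227 × 7/190 = 8.4. If every such subject attends Week 12, reported completion on SB206 is too low by 0 to 3.7 percentage points; if half attend, by 0 to about 1.8 points (0 to 4 subjects). The upper end borrows from regimens not used in this trial. Stops for pregnancy, lack of efficacy and the other non-qualifying reasons would add to it in either arm, but the documents give no separate rates for them.

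**Where the count is used.** SAP 9.1 feeds Table 14.1.1.1. The primary analysis takes all randomized subjects (SAP 8 and 10) and treats a missing response as non-response (SAP 10.4). Per-protocol membership rests on deviations (SAP 9.5). Neither refers to the 9.1 count.

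**The case against.** The best defence is that this is one descriptive line and no estimate or p-value depends on it. That is correct and sets the limit of the point. It is also fair that retention can be recovered elsewhere:

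- By-visit displays use subjects with non-missing data as the denominator (SAP 6).
- A Week 12 lesion count not performed is a possible significant deviation, and these are summarized by arm (SAP 9.5, Table 14.1.4).
- Disposition and lesion counts are listed by subject (Listings 16.2.1.1 and 16.2.6.1).

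The 9.1 line is therefore not the only evidence on retention. It is still the line labelled as 12-week study completion, and it is wrong for a group the protocol deliberately keeps in the study.

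A reader might go further in two ways that the documents do not support.

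**Clearance stoppers who exit early are counted as completers.** The exit condition removes anyone whose exit precedes the Week 12 visit. To defeat it, the early termination visit would have to be taken as the Week 12 visit, and SAP 7 maps it by study day instead. What remains is an unspecified case. No number of false completers can be derived, because the documents give no rate of clearance stops or of later exits.

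**The 9.1 flag contaminates the dropout sensitivity analysis.** SAP 11.1 plans "An analysis where the complete clearance response probability for each dropout prior to Week 12 will be independently generated" and does not define dropout, but nothing there points to 9.1. Loss of observed Week 12 counts through that route is conjecture.

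**Conclusion.** The point holds for the disposition summary. Under either reading of SAP 9.1, a subject who stops drug for a non-qualifying reason and attends Week 12 is reported as not completing 12 weeks of the study. A subject who stops for clearance and leaves without a Week 12 visit has no defined status.

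The likely size is small: 0 to about 8 SB206 subjects from adverse-event stops, assuming Phase 2 rates carry over and all of them attend Week 12, plus an unknown number from other reasons. A difference between arms is possible but not established, since none of the Phase 2 adverse-event stops was on the regimen tested here. The primary and secondary efficacy results are unaffected. The correction is worth making before unblinding because the stated rule gives a wrong retention count and the remedy costs almost nothing.

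**What to change.** In SAP 9.1, define 12-week study completion without reference to the treatment-stop reason: the subject has a lesion count assigned to the Week 12 analysis visit and dated within the SAP's own Week 12 window, Day 72 to 98.

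The date requirement matters. For suspected contact dermatitis, the Week 12/ET1 form is completed when drug stops. With no Study Exit form on that date, SAP 7 labels the visit Week 12 even if it took place on, say, Day 30. The window keeps such forms from qualifying. It also makes early leavers without a Week 12 count plain non-completers, so no fallback exit date is needed. A rule based only on a late Study Exit date would not do, because it would admit subjects who missed Week 12 and left later. The SAP should state that a Week 12 visit held after Day 98 falls outside this definition, if that is intended.

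Report treatment completion as a separate line, using the existing end-of-treatment reasons.

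The cost is about two sentences in the SAP, one derived flag and one extra row in Table 14.1.1.1. All the data are already collected.
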